Appendix A Schedule of Procedures *Continued*

Legend Continued

- 6 Stored at -80 °C for follow-up exploration of laboratory findings and/or AEs (e.g., measurement of cytokine and/or chemokine levels, measurement of additional markers of kidney function, measurement of antibodies, etc.) in this or subsequent clinical studies of ISIS 757456
- 7 If the platelet value, serum creatinine or liver enzyme tests are uninterpretable (e.g., due to clumping, hemolysis or quantity not sufficient) a repeat blood specimen should be re-drawn as soon as possible (ideally within 7 days) prior to next dose. Due to time constraints, a local lab draw is recommended if a repeat blood specimen is necessary to continue dosing at any time after Study Day 1 to Study Day 8.
- 8 Height at Screening only
- 9 Subjects who terminate treatment or post-treatment early from the study should be encouraged to participate in an early termination visit, at which time the Study D43 or Study D127 assessments should be conducted, respectively
- 10 Archived samples to be collected as well. Samples will be stored at -80 °C for follow-up exploration of laboratory findings and/or AEs in this or subsequent clinical studies of ISIS 757456
- 11 Fasting is not required at Screening visit. Fasted samples should be taken after fasting for at least 8 hours. During this time the patient can drink water and they should ensure that they consume sufficient water in order to not become dehydrated.

Time (time is in reference to Study Drug administration):

- a Pre-dose
- b Pre-dose, 3hr
- c Pre-dose, 2 hr
- d Pre-dose, 1, 2, 4, 6 hrs post-SC injection

APPENDIX B. LIST OF LABORATORY ANALYTES

Appendix B List of Laboratory Analytes

Based on emerging data from this or future studies, additional tests not listed below may be performed on stored samples to better characterize the profile of ISIS 757456 or other similar oligonucleotides.

Clinical Chemistry Panel	Screening Tests	Hematology	Inflammatory

 Sodium Potassium Chloride Bicarbonate Total protein Albumin Calcium Magnesium Phosphorus Glucose BUN Creatinine Creatinine Clearance Uric Acid Total bilirubin Direct (conjugated) bilirubin Indirect (unconjugated) bilirubin ALT AST Alkaline phosphatase Creatinine kinase GGT 	
 Hepatitis B surface antigen Hepatitis C antibody HIV antibody FSH (women only, if applicable) Serum βhCG (women only, if applicable) 
Coagulation
 
 aPTT (sec) PT (sec) INR 
Efficacy
 
 Plasma Angiotensinogen 
Pharmacokinetics¹
 
 ISIS 757456 levels in plasma 
Immunogenicity
 
 Anti-ISIS 757456 antibodies² 
Renal Urine Biomarkers
 
 NGAL³ NAG³ KIM-1 	
 Red blood cells Hemoglobin Hematocrit MCV, MCH, MCHC Platelets White blood cells WBC Differential (% and absolute) Neutrophils Eosinophils Basophils Lymphocytes Monocytes 
Exploratory
 
 Angiotensin II Renin (plasma renin activity) Renin (active renin mass concentration) Plasma Aldosterone Angiotensin I³ Angiotensin (1-7)³ Angiotensin III³ Angiotensin IV³ B-type natriuretic peptide³ Atrial natriuretic peptide³ Plasma Nephilysin³ Endothelin I³ 	
 Hs-CRP 
Urinalysis
 
 Color Appearance Specific gravity pH P/C Ratio (UPCR) Protein Blood Ketones Urobilinogen Glucose Bilirubin Leukocyte esterase Nitrate Microscopic examination² Angiotensinogen³ Albumin³ Creatinine³ Protein³ Sodium³ Cortisol³ Aldosterone³ A/C Ratio (UACR)³

¹ Plasma PK samples may also be used for profiling of drug binding proteins, bioanalytical method validation purposes, stability assessments, metabolite assessments, immunogenicity testing (or possibly for purposes of immunogenicity assay development and/or validation) or to assess other actions of ISIS 757456 with plasma constituents

² Will be performed on abnormal findings unless otherwise specified

³ May be analyzed

APPENDIX C. PK SAMPLING SCHEDULE

Appendix C PK Sampling Schedule

PK Sampling Schedule

Time Points for PK Blood Draws												
D1	D3	D8	D15	D22	D29	D36	D43	D50	D64	D78	D106	D127
Pre-dose, 1, 2, 4, 6 hrs post-D1 SC injection	Pre-dose	Pre-dose	Pre-dose	Pre-dose	Pre-dose	Pre-dose	Anytime	Anytime	Anytime	Anytime	Anytime	Anytime
Number of PK Blood Draws												
5	1	1	1	1	1	1	1	1	1	1	1	1

Note: Time is shown as hours relative to dose of Study Drug
 SC = subcutaneous
 D = Day

**APPENDIX D. GRADING SCALE FOR ADVERSE EVENTS RELATING
TO LABORATORY ABNORMALITIES**

Appendix D Grading Scale for Adverse Events Relating to Laboratory Abnormalities

The following grading recommendations for adverse events relating to lab test abnormalities and adverse events at the injection site are based upon the Common Terminology Criteria for Adverse Events (CTCAE) Version 5.0, November 2017.

Adverse Event	Mild	Moderate	Severe
Hematology			
aPTT prolonged	>ULN - 1.5 x ULN	>1.5 - 2.5 x ULN	>2.5 x ULN; bleeding
Eosinophils increased ¹	>ULN and >Baseline	-	Steroids Initiated
Fibrinogen decreased	<1.0 - 0.75 x LLN; if abnormal, <25% decrease from baseline	<0.75 - 0.5 x LLN; if abnormal, 25 - <50% decrease from baseline	<0.5 x LLN; if abnormal, ≥50% decrease from baseline
Hemoglobin decreased (Anemia)	Hemoglobin (Hgb) <LLN - 10.0 g/dL; <LLN - 6.2 mmol/L; <LLN - 100 g/L	Hgb <10.0 - 8.0 g/dL; <6.2 - 4.9 mmol/L; <100 - 80g/L	Hgb <8.0 g/dL; <4.9 mmol/L; <80 g/L; transfusion indicated
Hemoglobin increased**	Increase in >0 - 2 g/dL above ULN or above baseline if baseline is above ULN	Increase in >2 - 4 g/dL above ULN or above baseline if baseline is above ULN	Increase in >4 g/dL above ULN or above baseline if baseline is above ULN
INR increased	>1.2 - 1.5; >1 - 1.5 times above baseline if on anticoagulation	>1.5 - 2.5; >1.5 - 2.5 x baseline if on anticoagulation; monitoring only indicated	>2.5; >2.5 x baseline if on anticoagulation; dose adjustment indicated
Lymphocyte count decreased	<LLN - 800/mm ³ ; <LLN - 0.8 x 10 ⁹ /L	<800 - 500/mm ³ ; <0.8 - 0.5 x 10 ⁹ /L	<500 /mm ³ ; <0.5 x 10 ⁹ /L
Lymphocyte count increased	-	>4000/mm ³ - 20,000/mm ³	>20,000/mm ³
Neutrophil count decreased	<LLN - 1500/mm ³ ; <LLN - 1.5 x 10 ⁹ /L	<1500 - 1000/mm ³ ; <1.5 - 1.0 x 10 ⁹ /L	<1000/mm ³ ; <1.0 x 10 ⁹ /L
Platelet count decreased	<LLN - 75,000/mm ³ ; <LLN - 75.0 x 10 ⁹ /L	<75,000 - 50,000/mm ³ ; <75.0 - 50.0 x 10 ⁹ /L	<50,000/mm ³ ; <50.0 x 10 ⁹ /L
White blood cell decreased	<LLN - 3000/mm ³ ; <LLN - 3.0 x 10 ⁹ /L	<3000 - 2000/mm ³ ; <3.0 - 2.0 x 10 ⁹ /L	<2000/mm ³ ; <2.0 x 10 ⁹ /L
Chemistry			
Acidosis	pH <normal, but ≥7.3	-	pH <7.3
Alanine aminotransferase increased	>ULN - 3.0 x ULN if baseline normal 1.5 - 3.0 x baseline if baseline abnormal	>3.0 - 5.0 x ULN if baseline normal >3.0 - 5.0 x baseline if baseline abnormal	>5.0 x ULN if baseline normal >5.0 x baseline if baseline abnormal
Alkaline phosphatase increased	>ULN - 2.5 x ULN if baseline normal 2.0 - 2.5 x baseline if baseline abnormal	>2.5 - 5.0 x ULN if baseline normal >2.5 - 5.0 x baseline if baseline abnormal	>5.0 x ULN if baseline normal >5.0 x baseline if baseline was abnormal
Alkalosis	pH >normal, but ≤7.5	-	pH >7.5
Aspartate aminotransferase increased	>ULN - 3.0 x ULN if baseline normal 1.5 - 3.0 x baseline if baseline abnormal	>3.0 - 5.0 x ULN if baseline normal >3.0 - 5.0 x baseline if baseline abnormal	>5.0 x ULN if baseline normal >5.0 x baseline if baseline abnormal
Blood bilirubin increased	>ULN - 1.5 x ULN if baseline normal >1.0 - 1.5 x baseline if baseline abnormal	>1.5 - 3.0 x ULN if baseline normal >1.5 - 3.0 x baseline if baseline abnormal	>3.0 x ULN if baseline normal >3.0 x baseline if baseline abnormal
Cardiac troponin I increased	Levels above the upper limit of normal and below the level of myocardial infarction as defined by the manufacturer	-	Levels consistent with myocardial infarction as defined by the manufacturer

Adverse Event	Mild	Moderate	Severe
Cardiac troponin T increased	Levels above the upper limit of normal and below the level of myocardial infarction as defined by the manufacturer	-	Levels consistent with myocardial infarction as defined by the manufacturer
CD4 lymphocytes decreased	<LLN - 500/mm ³ ; <LLN - 0.5 x 10 ⁹ /L	<500 - 200/mm ³ ; <0.5 - 0.2 x 10 ⁹ /L	<200/mm ³ ; <0.2 x 10 ⁹ /L
CPK increased*	>ULN - <6 ULN	6 - 10 x ULN	>10 x ULN
Creatinine increased**	>ULN - 1.5 x ULN if baseline normal > 1.0 - 1.5 x baseline if baseline abnormal	>1.5 - 3.0 x ULN if baseline normal >1.5 - 3.0 x baseline if baseline abnormal	>3.0 x ULN if baseline normal >3.0 x baseline if baseline abnormal
GGT increased	>ULN - 2.5 x ULN if baseline normal 2.0 - 2.5 x baseline if baseline abnormal	>2.5 - 5.0 x ULN if baseline normal >2.5 - 5.0 x baseline if baseline abnormal	>5.0 x ULN if baseline normal >5.0 x baseline if baseline abnormal
Hypercalcaemia	Corrected serum calcium of >ULN - 11.5 mg/dL; >ULN - 2.9 mmol/L; Ionized calcium >ULN - 1.5 mmol/L	Corrected serum calcium of >11.5 - 12.5 mg/dL; >2.9 - 3.1 mmol/L; Ionized calcium >1.5 - 1.6 mmol/L; symptomatic	Corrected serum calcium of >12.5 mg/dL; >3.1 mmol/L; Ionized calcium >1.6 mmol/L; hospitalization indicated
Hyperglycemia††	Fasting glucose value ≥126 mg/dL (7.0 mmol/L)	Change in daily management to maintain fasting blood glucose <126 mg/dL (7.0 mmol/L); e.g. addition of oral antihyperglycemic agent; workup for diabetes	Insulin therapy initiated; hospitalization indicated
Hyperkalemia	>ULN - 5.5 mmol/L	>5.5 - 6.0 mmol/L; intervention initiated	>6.0; hospitalization indicated
Hypermagnesemia	>ULN - 3.0 mg/dL; >ULN - 1.23 mmol/L	-	>3.0 mg/dL; >1.23 mmol/L
Hypematremia	>ULN - 150 mmol/L	>150 - 155 mmol/L; intervention initiated	>155 mmol/L; hospitalization indicated
Hyperphosphatemia	Laboratory finding only and intervention not indicated	Noninvasive intervention indicated	Severe or medically significant but not immediately life-threatening; hospitalization or prolongation of existing hospitalization indicated
Hyperuricemia	>ULN without physiologic consequences	-	>ULN with physiologic consequences
Hypoalbuminemia	<LLN - 3 g/dL; <LLN - 30 g/L	<3 - 2 g/dL; <30 - 20 g/L	<2 g/dL; <20 g/L
Hypocalcaemia	Corrected serum calcium of <LLN - 8.0 mg/dL; <LLN - 2.0 mmol/L; Ionized calcium <LLN - 1.0 mmol/L	Corrected serum calcium of <8.0 - 7.0 mg/dL; <2.0 - 1.75 mmol/L; Ionized calcium <1.0 - 0.9 mmol/L; symptomatic	Corrected serum calcium of <7.0 mg/dL; <1.75 mmol/L; Ionized calcium <0.9 mmol/L; hospitalization indicated
Hypoglycemia‡	≥54 mg/dL - <70 mg/dL ≥3.0 mmol/L - <3.9 mmol/L	<54 mg/dL (3.0 mmol/L) AND no assistance required to actively administer carbohydrates, glucagon, or take other corrective actions	Requires assistance of another person to actively administer carbohydrates, glucagon, or take other corrective actions
Hypokalemia	<LLN - 3.0 mmol/L	symptomatic with <LLN - 3.0 mmol/L; intervention indicated	<3.0 mmol/L; hospitalization indicated
Hypomagnesemia	<LLN - 1.2 mg/dL; <LLN - 0.5 mmol/L	<1.2 - 0.9 mg/dL; <0.5 - 0.4 mmol/L	<0.9 mg/dL; <0.4 mmol/L
Hyponatremia	<LLN - 130 mmol/L	125-129 mmol/L and asymptomatic	125-129 mmol/L symptomatic; 120-124 mmol/L regardless of symptoms
Hypophosphatemia	Laboratory finding only and intervention not indicated	Oral replacement therapy indicated	Severe or medically significant but not immediately life-threatening; hospitalization or prolongation of existing hospitalization indicated
Lipase increased	>ULN - 1.5 x ULN	>1.5 - 2.0 x ULN; >2.0 - 5.0 x ULN and asymptomatic	>2.0 x ULN with signs or symptoms
Serum amylase increased	>ULN - 1.5 x ULN	>1.5 - 2.0 x ULN; >2.0 - 5.0 x ULN and asymptomatic	>2.0 x ULN with signs or symptoms

1 INTRODUCTION

This document provides a description of the study organization, study procedures, and the plan for the statistical analysis of the study data. Section 1 discusses study design, objectives, and endpoints; Section 2 provides the study procedures; Section 3 provides the detailed plan for the statistical analyses.

The purpose of this plan is to provide specific guidelines from which the analysis will proceed. Any deviations from these guidelines will be documented in the clinical study report (CSR).

Within this document, the terms 'patient' and 'subject' are both used to describe the individual who enrolls in this study.

1.1 Study Overview

This will be a Phase 2, double-blind, randomized, placebo-controlled study of ISIS 757456 conducted in mild hypertensive subjects on an ACEi/ARB and an additional hypertensive medication. Subjects will be stratified based on a screening plasma AGT concentration ($\leq 30 \mu\text{g/mL}$ vs. $> 30 \mu\text{g/mL}$) and randomized in a 2:1 ratio to receive a once-weekly subcutaneous (SC) treatment and an additional loading dose on Study Day 3 with either ISIS 757456 80 mg or placebo for 6 weeks.

[figure not shown]
All subjects will complete a 13-week Post-Treatment Period. In the Post-Treatment Period, should a subject's sitting BP on home monitoring exceed 140 mmHg systolic or 100 mmHg diastolic on 2 consecutive days (confirmed by triplicate measurement at the Study Center), the subject's initial hypertension (HTN) medication(s) may be added back per Investigator and Sponsor Medical Monitor judgment and the subject will continue to be followed per protocol in the study.

[REDACTED] All Study Drug injections will be SC administered in the clinic.

This study will be conducted at multiple centers in the United States. Approximately 30 subjects are planned to be enrolled in this study.

The study will consist of screen, run-in, washout (WO), treatment, and post-treatment. The overall length of a subject's participation will be approximately 25 weeks (up to 3 weeks for screening, 1-week run-in, 2 weeks for WO, a 6-week Treatment Period, and 13 weeks of Post-Treatment Evaluation Period).

The study design and treatment schema are depicted as follows:

1.2 Objective

1.2.1 Primary Objective(s)

- To evaluate the effect of ISIS 757456 subcutaneous (SC) injection on plasma angiotensinogen concentration

1.2.2 Secondary Objective(s)

- To evaluate the effect of ISIS 757456 on in-clinic systolic blood pressure over time in Treatment and Post-Treatment Periods

1.2.3 Safety Objectives

- To evaluate the safety and tolerability of ISIS 757456 vs. placebo

1.2.4 Exploratory Objectives

- To evaluate the effect of ISIS 757456 on at-home blood pressure over time in the Treatment and Post-Treatment Periods
- To evaluate the exploratory effects of ISIS 757456 administered subcutaneously {e.g., angiotensin II, renin [Plasma renin activity (PRA); active renin mass concentration (ARC)], plasma aldosterone}
- To evaluate the pharmacokinetics (PK) of ISIS 757456 (as total Full Length ASO, including fully conjugated, partially conjugated, and unconjugated ISIS 757456) administered subcutaneously in subjects with hypertension
- To evaluate potential PK/PD correlation with relevant biomarkers

1.3 Endpoints

1.3.1 Primary Endpoint

- Percent change in plasma angiotensinogen from Baseline to Study Day 43 (Week 7) compared to placebo

1.3.2 Secondary Endpoints

- Change on in-clinic SBP from Baseline to each scheduled, post-Baseline visit
- Change and percent change in plasma angiotensinogen from Baseline to each scheduled, post-baseline visit

1.3.3 Safety Endpoints

- Incidence and severity of treatment-emergent adverse events (TEAE) (including hypotension and orthostatic hypotension), use of concomitant medications, laboratory assessments, ECG, and vital signs

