8.5.3. Safety Monitoring Rules for Blood Pressure

1. In the event of a SBP \leq 100 mmHg a second measurement must be done within a 30-minute period. If the subject's SBP is \leq 100 mmHg within the 30-minute period, an additional BP measurement should be taken within 48 hours at the Study Center, regardless of whether the initial BP measurements were taken in clinic or at home. If the subject then experiences an additional SBP measurement \leq 100 mmHg (confirmed by triplicate measurement at the Study Center), or if the subject is symptomatic (i.e., dizziness, light-headedness, clammy skin, fatigue, blurry vision), the dose will be withheld. Vital signs should be confirmed, and orthostatic hypotension assessment should be performed (See Section 6.1.1.2). In addition, the subject will have home BPM 2 times per day for 1 week. Subject should orally hydrate with 1-liter fluids, including fluids with electrolyte solution (sports drink, etc.). If the subject is symptomatic the Investigator should consider admitting for observation and consider instituting intravenous (IV) hydration with 1-liter normal saline solution and reassess symptoms and orthostatic hypotension assessment. When SBP is $>$ 100 mmHg and is asymptomatic then patient should continue dosing. If the patient has orthostatic vital signs and is asymptomatic, the dose should be withheld until orthostatic hypotension is resolved. The subject will continue to be followed per protocol in the study. Follow-up for subjects that screen fail due to blood pressure inclusion criteria (see Section 5.1) will not be necessary.

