9.3. Definitions

9.3.1. Adverse Event

An adverse event (AE) can be any unfavorable and unintended sign (including an abnormal laboratory finding, for example), symptom, or disease temporally associated with the use of medicinal (investigational) product, whether or not the AE is considered related to the medicinal (investigational) product.

An AE can therefore be any of the following:

- Any unfavorable and unintended sign (including an abnormal laboratory finding), symptom, or disease temporally associated with the use of a medicinal product, whether or not considered related to the medicinal product
- Any new disease or exacerbation of an existing disease (a worsening in the character, frequency, or severity of a known condition)
- Recurrence of an intermittent medical condition (e.g., headache) not present at Baseline
- Any deterioration in a laboratory value or other clinical test (e.g., ECG, X-ray) that is associated with symptoms or leads to a change in study treatment or concomitant treatment or discontinuation from Study Drug
- Adverse events that are related to a protocol-mandated intervention, including those that occur prior to assignment of study treatment (e.g., screening invasive procedures such as biopsies)

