3 ANALYSIS PLAN

3.1 General Overview of Analyses

Descriptive summary statistics including number of subjects, mean, median, standard deviation, standard error of mean, 25th percentile, 75th percentile, minimum, and maximum for continuous variables, and counts and percentages for categorical variables will be used to summarize most data. All statistical tests will be conducted using 2-sided tests with 5% Type I error rate unless otherwise stated.

[figure not shown]
PK parameters will be summarized using include number of subjects, mean, standard deviation, coefficient of variation (CV), geometric mean, median, minimum, and maximum.

Baseline definition:

The baseline for plasma AGT will be define as the average of all values on or after Study Day -7 and prior to the first dose of Study Drug. The baseline for all other assessments will be defined as the last non-missing measurement prior to the first dose, unless otherwise specified.

Analytical visits:

Data will be summarized using the visit labels provided in the data. Multiple results with the same visit label will be averaged. Results with visit labels as "Unscheduled" will not be included in the by-visit summary tables and figures except for determining baseline and the analysis of confirmed ALT/AST category (see section 3.7.3) but will be presented in data listings.

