3.7.2 Adverse Events

The incidence of AEs will be summarized by Medical Dictionary for Regulatory Activities (MedDRA) version 21.1 preferred term and system organ class for:

- Any treatment emergent adverse events
- Related treatment emergent adverse events. Related is defined as “Related”, “Possible”, or missing relationship to study drug
- Any treatment emergent adverse events by severity. At each level of subject summarization, a subject is classified according to the highest severity if the subject reported one or more events. Adverse events with missing severity will be categorized as “Missing” for this summary
- Serious treatment emergent adverse events

SAEs and TEAEs that lead to study discontinuation or investigational drug discontinuation will be listed separately. Non-treatment emergent adverse event will be flagged in the data listing.

An adverse event will be regarded as treatment emergent if it is present prior to receiving the first dose of study drug or placebo and subsequently worsened, or is not present prior to receiving the first dose of study drug or placebo but subsequently appeared.

If there is no “Formlink” link, and the AE (start date/time) occurs after the subject’s first dosing date/time, then the AE is treatment-emergent. Otherwise, if the AE (start date/time) occurs prior to the subject’s first dosing date/time, then the AE is not treatment-emergent.

If there is a “Formlink” link between two AE records, then we compare them pairwise, and consider two cases, where we compare the AE severity (mild/moderate/severe) between the two records in the pair. We chronologically order the 2 records (by AE start date) and refer to the “first” and “second” AEs.

Case 1: The first AE record in the pair occurs before first dosing, and the second record occurs after dosing.

If the AE severity on the second record is worse than the severity on the first record, then only count the second AE as treatment-emergent. But, if the severity improves (second record severity is less severe than the first record severity), then neither record is counted as treatment-emergent.

Case 2: Both AE records in the pair occur after first dosing.

If the AE severity on the second record is worse than the severity on the first record, then count both records as treatment-emergent. But, if the severity improves, then only count the first record as treatment-emergent.

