3.7.4 Vital Signs

Vital signs will include heart rate, respiratory rate, body temperature, BMI and systolic and diastolic blood pressure. Vital signs will be summarized by treatment group for vital sign values as well as the change and percent change from baseline at each post-baseline visit.

The study provided at-home blood pressure monitor (Omron Device) is used to assess each at-home triplicate measurement. The device automatically conducts three successive blood pressure assessments with 60 seconds in between each measurement. The device records one time for the triplicate assessments - the time provided is the start time of the triplicate sequence, therefore, the data reported in the subject diary and in EDC has one collection time for all three blood pressure assessments. The triplicate average will be based on the first 3 blood pressure assessments.

3.7.5 12-Lead Electrocardiograms (ECG)

Safety 12 lead ECG will be performed in triplicate at the visits indicated in the protocol Schedule of Procedures. The baseline is defined as the average of the triplicate prior the first dose of study drug.

The ECG data will include ventricular rate (VR), PR interval, QRS duration, QT, and corrected QT intervals, and overall interpretation.

For the continuous variables above, descriptive statistics (n, mean, standard error, standard deviation, median, 25th percentile, 75th percentile, minimum and maximum) of the average of triplicate results at each study visit, as well as the change and percent change from Baseline to each study visit, will be presented in summary tables; for the categorical responses to overall

interpretation, the worst of triplicate results and the associated findings at each visit will be summarized by counts and percentages. All the ECG data collected in triplicate will be listed.

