5 APPENDICES

5.1 Visit window for prior-treatment visit

For the at-home blood pressure results summary, the weekly average approach is applied, which is similar to the post-baseline summary approach. If there are multiple results on the same day for a subject, the average daily values were calculated first. Daily subject values within consecutive seven-day periods are averaged to determine the subject weekly result value. The visit window is as following: subject values from Days -21 to -15, -14 to -8, and -7 to -1 inclusively represent Week -3 (Run-In), Week -2 (washout first week) and Week -1 (washout second week), respectively.

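### The hypotension endpoint rests on investigator-reported AE terms; no planned output counts, by arm, the subjects whose systolic pressure crossed the protocol's low-BP action values

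*Combined protocol and SAP*

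**What the plan says.** **Endpoint.** SAP 1.3.3 and Protocol 1.2.3 name "Incidence and severity of treatment-emergent adverse events (TEAE) (including hypotension and orthostatic hypotension"). Vital signs are a separate item in the same endpoint.

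**AE analysis.** SAP 3.7.2: "The incidence of AEs will be summarized by Medical Dictionary for Regulatory Activities (MedDRA) version 21.1 preferred term and system organ class for" TEAEs overall, related, by severity, and serious. Protocol 9.3.1 defines an AE as "any unfavorable and unintended sign (including an abnormal laboratory finding, for example), symptom, or disease temporally associated" with use of the product. It gives no BP cut-off.

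**BP action values.** Protocol 8.5.3 acts on SBP ≤100 mmHg. If a repeat within 30 minutes is also low, "an additional BP measurement should be taken within 48 hours at the Study Center". Protocol 8.6.5 acts on SBP ≤90 mmHg with symptoms.

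**BP outputs.** SAP 3.7.4: "Vital signs will be summarized by treatment group for vital sign values as well as the change and percent change from baseline". These summaries are given visit by visit. SAP 3.1 says that unscheduled results "will not be included in the by-visit summary tables and figures except for determining baseline and the analysis of confirmed ALT/AST category"; the same sentence sends them to the data listings. For home BP, SAP 5.1: "Daily subject values within consecutive seven-day periods are averaged to determine the subject weekly result value". The change in that weekly average is an exploratory endpoint (SAP 1.3.4, analysed in 3.5.3).

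**Comparator.** SAP 3.7.3 tabulates, by arm, the number and percent of subjects with confirmed ALT/AST above 3 and 5 times ULN.

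**The concern.** Hypotension and orthostatic hypotension are the only TEAEs singled out in the safety endpoint, and Protocol 2.2 lists hypotension among the complications of combining RAAS agents. The protocol collects many BP readings and attaches numeric action values to low ones. One would expect at least one output to say how many subjects in each arm reached those values, and there is none.

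The by-arm comparison of hypotension therefore depends on how each site turns a low reading into an AE term. With about 20 active and 10 placebo subjects, one or two events recorded differently would change the picture. The readings that could check the AE counts are in the database, but no planned summary uses them for this purpose.

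**Working it through.** The plan gives no figure to reproduce. The check traces where a low reading can surface, then illustrates the effect of weekly averaging.

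**1. Routes from a low reading to an output**

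| Source | Planned output | By-arm count of subjects crossing ≤100 or ≤90? |
|---|---|---|
| AE record (SAP 3.7.2) | TEAE incidence by preferred term and severity | Only if the site entered an AE; no BP value requires it |
| Scheduled clinic BP (SAP 3.1, 3.7.4) | By-visit statistics, including minimum and maximum | No; the minimum shows the lowest value, not how many subjects |
| Unscheduled clinic BP (SAP 3.1) | Listing | No; the exceptions are baseline and confirmed ALT/AST |
| Home BP (SAP 3.5.3, 5.1) | Weekly average; readings after antihypertensive restart leave the exploratory comparison | No |
| Orthostatic test (Protocol 6.1.1.2; Appendix A footnote 2) | None specified; required at Screening, later triggered by Protocol 8.5.3 | No |

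The 48-hour Study Center reading will probably be unscheduled unless it falls on a planned visit. The documents do not say how it is labelled.

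**2. Where AE recording is least certain.** Protocol 9.3.1 also counts deterioration in a clinical test that brings symptoms or changes study or concomitant treatment. The last dose is on Day 36 and the last visit on Day 127, so 127 − 36 = 91 days (13 weeks) have no dose to withhold. An asymptomatic crossing then that changes no other treatment is not clearly captured by that criterion.

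**3. Averaging arithmetic.** With *k* home days in a week, one of them at *L* mmHg, the weekly mean exceeds 100 when the other days average more than (100*k* − *L*)/(*k* − 1). Protocol 6.1.1.3 asks for three days a week and allows one to be missed.
- *L* = 90, *k* = 3: (300 − 90)/2 = 105.
- *L* = 90, *k* = 2: (200 − 90)/1 = 110.
- Example: (98 + 125 + 125)/3 = 116.

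**4. Simulation under assumptions.** The documents give no SD for home BP. Three independent normal daily SBPs were drawn, with 400,000 weeks per scenario.

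| Assumed mean, SD | P(any day ≤100) | P(weekly mean ≤100, given any) |
|---|---|---|
| 110, 8 | 0.284 | 0.053 |
| 110, 10 | 0.402 | 0.101 |
| 110, 12 | 0.491 | 0.152 |
| 120, 8 | 0.019 | 0.000 |
| 120, 10 | 0.067 | 0.004 |
| 120, 12 | 0.136 | 0.014 |
| 130, 8 | 0.000 | 0.000 |
| 130, 10 | 0.004 | 0.000 |
| 130, 12 | 0.019 | 0.001 |

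The share of such weeks whose mean stays above 100 runs from 1 − 0.152 = 0.848 to essentially 1. A fall lasting the whole week would not be masked, so correlation between days would lower these shares.

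**5. Would the table have anything to show?** With 2:1 allocation of about 30 subjects (20 and 10), P(at least one affected) = 1 − (1 − *p*)^*n*, for assumed true rates *p*:

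| *p* | Active, *n* = 20 | Placebo, *n* = 10 |
|---|---|---|
| 5% | 64% | 40% |
| 10% | 88% | 65% |
| 20% | 99% | 89% |

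**The case against.** The strongest reply is that the endpoint is a TEAE incidence and the SAP analyses it as one. Visit-label and averaging rules never touch AE records. This stands, and it rules out several stronger readings that a reader might infer.

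- *That low readings vanish.* They do not. SAP 3.1 keeps unscheduled results in listings, and Protocol 10.6 lists all CRF data for randomized subjects. The Medical Monitor reviews home and clinic BP throughout (Protocol 6.1.4, 6.1.5), and listings for about 30 subjects can be read case by case.
- *That 100 and 90 mmHg define hypotension.* They are monitoring and stopping triggers. The only numeric definition is for orthostatic hypotension (Protocol 6.1.1.2), which needs a supine and standing test.
- *That sites may ignore any low reading.* A reading that causes a dose to be withheld fits Protocol 9.3.1 on a natural reading, and 9.4.3.3 provides for recording an interruption.
- *That an extreme clinic value is hidden.* At a scheduled visit a very low value would normally show as the arm's minimum, because SAP 3.1 includes minimum and maximum. Only results sharing a visit label are averaged first.
- *That home BP is excluded from safety.* SAP 3.7.4 describes how home triplicates are averaged, so exclusion cannot be shown. The only summary described is weekly, and the windows written out in SAP 5.1 are pre-treatment, with post-baseline handling called similar.
- *That the SAP breaks a protocol promise.* Protocol 10.6.2 says only that vital signs will be tabulated by treatment group.

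None of this yields a by-arm count of subjects, and listings do not make that comparison. The SAP made the opposite choice for ALT/AST, with a threshold table and an explicit exception that admits unscheduled results.

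**Conclusion.** The point holds as a gap in the safety outputs, not as a failure to analyse the endpoint. Hypotension incidence will come from investigator-reported terms with no BP value tied to them, and no planned BP output gives an objective by-arm comparison.

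The size cannot be stated as a change to any figure in the plan. The masking range of about 85 to 100% rests on assumed means and SDs and on independent days; it concerns the home-BP summary only, not the TEAE tables or listings. The chances of seeing an affected subject rest on assumed rates. This is a worthwhile, low-cost improvement.

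**What to change.** Add to SAP 3.7.4, for the Safety Set from first dose to last visit:

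- A by-arm table of the number and percent of subjects with any, and with confirmed, SBP ≤100 mmHg and SBP ≤90 mmHg. Use scheduled and unscheduled clinic readings and each daily home triplicate mean, not the weekly average. Show results separately before and after any antihypertensive restart.
- In the same table, subjects with any event-triggered orthostatic result meeting the definition in Protocol 6.1.1.2.
- A listing of each subject's lowest SBP beside any hypotension AE.

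State what counts as confirmed by reference to the Study Center confirmation in Protocol 8.5.3 and 8.6.5, and extend the SAP 3.1 exception for unscheduled results to this table. Rows for >170 mmHg systolic or >110 mmHg diastolic are optional and do not bear on hypotension.

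The cost is SAP wording, one table and one listing from data already collected. Some isolated low home readings will be counted, which is why any and confirmed crossings are shown separately. No clinical rule is changed.
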